**RESEARCH PLAN****Title: Effects of sildenafil on CFTR-dependent ion transport activity in subjects with mild-moderate CF lung disease**

Sildenafil is an attractive agent for further study in cystic fibrosis (CF). Preclinical studies have demonstrated that sildenafil can correct the pH and sodium abnormality in CF cells, improve F508del CFTR trafficking and potentiate CFTR dependent Cl transport, and may also exhibit anti-inflammatory properties. We have shown it is well-tolerated in a pilot trial of CF patients, and it also has a well-established safety profile in severe lung disease. We propose to test the *in vitro* ability of sildenafil to improve ion transport in the setting of abnormal CFTR in human CF subjects.

**Hypothesis: Systemic administration of sildenafil to patients with mild-to-moderate CF lung disease will correct CFTR-mediated sodium (Na) hyperabsorption, and CFTR-dependent anion secretion, resulting in improvements in sodium measurements in nasal potential difference and sweat electrolyte analysis collected by pilocarpine iontophoresis.**

**Aim 1. Test if systemically administered phosphodiesterase inhibitors improve ion transport in CF**

- a. Measure Na+ and Cl conductance by NPD before and after therapy
- b. Measure Na+ and Cl concentration in sweat utilizing pilocarpine iontophoresis before and after therapy

**Aim 2. Evaluate the effect of sildenafil on clinically relevant outcomes in subjects with CF**

- a. Evaluate the effect of sildenafil on lung function in subjects with CF
- b. Evaluate the effect of sildenafil on weight in subjects with CF
- c. Evaluate the effect of sildenafil on pulmonary exacerbations in subjects with CF
- d. Evaluate the effect of sildenafil on quality of life in subjects with CF

**Aim 3. Further evaluate the safety and tolerability of sildenafil in subjects with CF**

- a. Evaluate the effect of sildenafil on treatment emergent adverse events
- b. Evaluate the effect of sildenafil on change in clinical laboratory measures, vital signs and physical exam findings

**Background*****In vitro* effects of phosphodiesterase inhibitors on ion transport, pH and inflammation in CF**

CF is caused by mutations in the Cystic Fibrosis Transmembrane Conductance Regulator (CFTR) gene, which encodes a protein of the same name. CFTR belongs to a family of proteins involved in ion transport. It is known to act as a chloride transport channel, and also to regulate other ion channels, including the epithelial sodium channel, ENaC. Defective transport of sodium and chloride across the respiratory epithelial cell membrane leads to dehydration of the periciliary liquid and mucous layers overlying the surface epithelium, resulting in defective mucociliary and cough clearance in the lung.

Alterations in ion transport due to absent or deficient CFTR function have also been shown to effect organelle pH. Poschet *et al* demonstrated that increased Na+ efflux (resulting from loss of inhibition by dysfunctional CFTR) results in intracellular positive charge loss. To compensate for this charge loss and neutralize the membrane potential, there is excessive H+-ATPase action, resulting in trans-Golgi network (TGN) acidification (Figure 1). Inhibition of ENaC by amiloride or the Na+/H+ pump (by acetylstrophanthidine with H+ ion substitution) lead to improvements in pH, thus providing evidence that Na+ transport is crucial in organellar hyperacidification.

One recently described consequence of intracellular hyperacidification in CF is increased activity of the proprotein convertase, furin. Furin, found both in the TGN and at the plasma membrane, activates ENaC by direct proteolytic processing of ENaC subunits. Proteolytic cleavage of ENaC is requisite for ENaC mediated sodium transport thought to play a causative role in CF lung disease. In addition to effects on furin and ENaC, trans-Golgi acidification has also been postulated to contribute to CF pathogenesis by altering the function of glycosylation enzymes key to normal processing of the CFTR protein. The glycosylation enzymes such as sialyltransferases and fucosyltransferases are pH sensitive and are crucial to the processing of wtCFTR. As

*Pseudomonas aeruginosa* is thought to exhibit increased affinity for respiratory mucins due to disordered glycosylation pathways (undersialylated glycoconjugates), altered glycosylation due to absent CFTR activity may also contribute to the predisposition to *P. aeruginosa* highly characteristic of CF lung disease.

Given the multiple detrimental effects of TGN hyperacidification, including excess furin activity, disordered glycosylation (leading to *P. aeruginosa* predisposition), and possibly dysregulated inflammation (see also below), the TGN pathway represents a potential therapeutic target in CF to reconcile a number of the downstream effects of CFTR dysfunction. As correction of organelle pH would be expected to reduce excessive Na+ transport on the airway surface by blocking ENaC mediated sodium transport through inhibition of furin, this strategy represents a means to block excessive sodium absorption thought to contribute to disease pathogenesis.

PDE inhibitors (PDEi) have been reported to reduce excessive sodium transport in the CF cell by increasing cellular cGMP and therefore, restoring ENaC inhibition; use of this drug class therefore represents an attractive approach to address both TGN hyperacidification and the sodium transport abnormality found in the CF airway. Recently, our laboratory demonstrated that the treatment of CF cell lines (including those from  $\Delta F508$  homozygous and heterozygous patients) with the archetype PDE 5 inhibitor sildenafil led to increased intracellular cyclic guanosine monophosphate (cGMP), and corrected endosomal hyperacidification in CF respiratory epithelial cells (Figure 1). As PDEis have demonstrated other effects likely beneficial in CF (see below), and are available by systemic administration, this class of agents may have inherent advantages over other strategies (such as inhaled medications) intended to inhibit ENaC function.

Recent studies have also shown that PDEi can potentiate CFTR-mediated chloride transport activity and also correct surface localization of F508del CFTR. Cobb *et al* showed that PDEis, including sildenafil, stimulate CFTR-dependent chloride transport in polarized airway cell monolayers expressing wild-type CFTR. Importantly, this effect was dose-dependent, and for two of the agents tested, achievable at concentrations below peak serum levels that occur with dosing used in systemic treatment of pulmonary hypertension. Researchers have also studied the effects of sildenafil on CFTR trafficking in airway epithelial cells from CF and non-CF patients. Exposure to sildenafil led to rescue of F508del CFTR to the apical membrane as measured by immunofluorescence localization. In related work, Robert *et al* demonstrated that a structural analog of sildenafil optimized for cell culture experiments, KM11060, partially restored  $\Delta F508$  trafficking in baby hamster kidney cells. In our lab, using nasal mucosal tissue from  $\Delta F508$ del mice, we showed that transepithelial Cl currents improved following treatment with sildenafil. More recently, Lubamba *et al* restored CFTR-dependent chloride transport using the nasal potential difference (NPD) assay in F508del mice, substantiating the approach that PDEi can restore both the cellular localization and activity of F508del CFTR in the airway.

[figure not shown]
Sildenafil has also been shown to have anti-inflammatory effects that may be beneficial in the context of the pro-inflammatory environment of the CF lung. For example, in CF respiratory epithelial cells, we demonstrated that the excessive proinflammatory response to *P. aeruginosa* exposure could be reversed by treatment with sildenafil. Toward *et al* demonstrated that pretreatment with sildenafil inhibited LPS-induced airway hyperreactivity, white cell influx and NO dysfunction in two guinea pig models of airway disease. Finally, DBA/2 mice sensitive to *P. aeruginosa* were fed a diet with or without sildenafil. Following aerosol-delivered *P. aeruginosa* respiratory infection, myeloperoxidase in lung homogenates (a reflection of neutrophil infiltration) was reduced by  $42 \pm 11\%$  ( $p=0.047$ ) in animals who received sildenafil-containing diets.

In concert, these studies suggest that PDEis might be a way to reconcile both the sodium and chloride ion transport defects present in the CF lung, and may also address other downstream effects resulting from TGN hyperacidification found in CF, including disordered CFTR glycosylation, a predisposition to *P. aeruginosa*, and excessive inflammation. Based on the *in vitro* data suggesting a possible role for PDEi as anti-inflammatories in CF, we designed a single site open-label dose escalation study (Clinicaltrials.gov No.: NCT00659529) to evaluate the safety, efficacy and pharmacokinetics of sildenafil in subjects with mild to moderate CF lung disease. On study day 1, subjects underwent exhaled breath condensate (EBC) measurement, lung function and routine laboratory testing, completed the CF Health Related Quality of life questionnaire (CFQ-R), and had sputum collected for bacterial counts and sputum biomarkers. Subjects received oral sildenafil 20 or 40 mg p.o. t.i.d. for 6 weeks, and all evaluations were repeated at the end of 6 weeks. Twenty subjects completed the

study. There were no drug-related serious adverse events, and side effects were generally mild and consistent with those previously reported. There was improvement in the primary endpoint, mean sputum elastase ( $p < 0.03$ ), which is a sensitive measure of CF airway inflammation and has been shown to predict lung function decline in patients with CF. There was also a non-significant trend towards improvement in sputum IL-8 ( $p = 0.13$ ). There was no difference in EBC pH, the respiratory score of the CFQ-R, or sputum microbiology ( $p = 0.44$ ,  $p = 0.88$  and  $p = 1.0$ , respectively).

Given the relative ease of testing this approach due to the clinical availability of sildenafil and other PDEis, these results suggest a strong need to also study the ion transport effects of sildenafil in CF. This study represents an excellent opportunity to capitalize on the safety and tolerability assessments already completed at our institution.

**Figure 1. Model of endosomal hyperacidification in cystic fibrosis respiratory epithelial cells and its correction by NO and phosphodiesterase 5 inhibitors.** Shades of pink, endosome luminal acidification levels (darker color—lower pH); green boxes, active pumps or open channels; red boxes, inactive channels; yellow boxes, normal pump or channel activity. (A) In normal human respiratory epithelial cells, the CFTR inhibits sodium channels (ENaC), resulting in positive charge build-up as vacuolar H+ ATPase pumps protons into the endosomal lumen. The proton pump is sensitive to transmembrane potential build-up, and shuts down, resulting in physiologically normal, mild luminal acidification of the endosome. (B) In CF respiratory epithelial cells, with defective CFTR, ENaC is no longer inhibited by CFTR, which allows efflux of sodium as the protons are being pumped into the endosomal lumen by the proton pump. The sodium efflux dissipates membrane potential, allowing the vacuolar H+ ATPase to extend its proton-pumping action, thus causing mild hyperacidification. (C) As shown in this work, nitric oxide (NO) can correct endosomal hyperacidification in CF respiratory epithelial cells, by cGMP-dependent block of sodium transport through amiloride-sensitive channel ENaC. Hyperacidification can be corrected using sildenafil or other inhibitors specific for cGMP PDE5. CF, cystic fibrosis; CFTR, CF transmembrane conductance regulator; cGMP, cyclic GMP; PDE5, phosphodiesterase.

### Sildenafil as candidate drug

Protein kinase G-dependent smooth muscle relaxation occurs in response to elevated levels of cGMP. Inhibition of phosphodiesterase type 5 (PDE-5,) which is responsible for degradation of cGMP, or stimulation with nitric oxide (NO) can cause this effect. Sildenafil (Revatio, Pfizer) is a PDE-5 inhibitor. Sildenafil-induced increased cGMP concentration leads to pulmonary vasculature smooth muscle relaxation. It is this effect that is key in treatment of pulmonary hypertension by sildenafil.

A case study reported on the use of sildenafil in a patient with severe CF lung disease (genotype  $\Delta F508/G551D$ , FEV1 1.051, 23% predicted) complicated by exercise-induced pulmonary hypertension. Treatment with 1 week of oral sildenafil 25 mg twice a day, followed by 4 months of 25 mg four times a day, lead to physiological improvement, and decreased subjective complaints of dyspnea and chest pain with exertion within 2 weeks of starting therapy. Improvements in exercise tolerance were increased further after 4 months of therapy. Sildenafil was well-tolerated with no adverse events. Although these effects were attributed to the reduction in pulmonary artery pressure, the more prolonged and sustained improvement suggests the possibility for a more global effect on the ion transport abnormality, and also demonstrates the relative safety of this agent even in individuals with severe lung disease.

### Pharmacokinetics of sildenafil

Sildenafil is rapidly absorbed following oral administration in the fasting state with peak plasma concentrations occurring within 30-120 minutes (median 60 minutes) of administration. It is metabolized by the hepatic microsomal isoenzymes, CYP3A4 and cytochrome p450 2C9 (CYP2C9) to its major metabolite N-desmethyl sildenafil. The metabolite accounts for approximately 20% of the pharmacologic effects of sildenafil. Both sildenafil and N-desmethyl sildenafil have a half-life of approximately 4 hours.

Sildenafil (Revatio®) is FDA-approved for treatment of pulmonary hypertension at an oral dose of 20 mg three times per day. In a large trial (n=278) of use of sildenafil for pulmonary hypertension published in the *New England Journal of Medicine*, escalating doses of sildenafil were used for 12 weeks (20 mg three times a day, 40 mg three times a day, and 80 mg three times per day.) There was no dose-related effect on the primary outcome. Although the initial group of subjects was treated for 12 weeks, improvements in the primary outcome were seen at 4 weeks.

In summary, laboratory evidence that sildenafil can correct the pH and sodium abnormality in CF cells, improve F508del CFTR trafficking and potentiate CFTR dependent Cl transport, and may also exhibit anti inflammatory properties, combined with the well-established safety profile of sildenafil in severe lung disease make it an attractive agent to study in patients with CF. To date, studies have examined the *in vitro* ability of sildenafil to improve ion transport in the setting of abnormal CFTR; we propose to evaluate effects in human CF subjects.

**Aim 1. Test if systemically administered phosphodiesterase inhibitors improve ion transport in CF**

- c. Measure Na+ and Cl conductance by NPD before and after therapy
- d. Measure Na+ and Cl concentration in sweat utilizing pilocarpine iontophoresis before and after therapy

**Aim 2. Evaluate the effect of sildenafil on clinically relevant outcomes in subjects with CF**

- a. Evaluate the effect of sildenafil on lung function in subjects with CF
- b. Evaluate the effect of sildenafil on weight in subjects with CF
- c. Evaluate the effect of sildenafil on pulmonary exacerbations in subjects with CF
- d. Evaluate the effect of sildenafil on quality of life in subjects with CF

**Aim 3. Further evaluate the safety and tolerability of sildenafil in subjects with CF**

- a. Evaluate the effect of sildenafil on treatment emergent adverse events
- b. Evaluate the effect of sildenafil on change in clinical laboratory measures, vital signs and physical exam findings

Primary Endpoints

Na+ conductance by nasal potential difference (within subject change in maximum basal PD)

Secondary Endpoints

Other measures of Na transport (mean basal PD, end-ringers profusion PD, change in PD with amiloride)  
 Cl conductance by NPD (total Cl conductance, change in PD with chloride free solution, change in PD with isoproteronol, total change in NPD (delta NPD))  
 Sweat Na+ by pilocarpine iontophoresis  
 Sweat Cl concentration by pilocarpine iontophoresis  
 Pulmonary function by spirometry  
 Lung clearance index  
 Exhaled nitric oxide (eNO)  
 Sputum nitric oxide metabolites  
 Safety and tolerability (including laboratory studies, CFQ-R)

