Subjects will be randomized in a 2:1 fashion to sildenafil or placebo. The randomization protocol will be created by [name] (Professor and Head, Division of Biostatistics and Bioinformatics, National Jewish Health). The protocol will be provided directly to the study pharmacist, who will communicate randomization to the coordinator at the research site.

Dosing

During the course of the study, patients will receive 4 weeks of therapy: 28 days of placebo orally t.i.d. or 28 days of days of sildenafil orally t.i.d. Dosing of sildenafil will be escalated weekly (20 mg orally t.i.d for the first week, 40 mg orally t.i.d. for the second through fourth weeks.) Patients receiving placebo will have sham dose escalation to maintain blinding. Patients not tolerating dose escalation will be discontinued from the study.

Screening visit (visit 1; Day -14-0):

Prior to conducting any study-related activities, written informed consent/assent will be obtained, signed and dated by the subject and/or parent/guardian.

A medical history including diagnosis of CF, current medications and other relevant past medical history will be obtained, and a complete physical exam will be performed by the principal investigator including nasal exam rating (NER), height, weight, temperature, blood pressure, respirations and baseline pulse oximetry will be recorded. Any abnormal findings will be documented. Clinical laboratory tests will be performed including CBC with differential, chemistry profile, INR (total of 10cc of blood), and a urine pregnancy test (for females of child-bearing potential). A baseline EKG will be obtained. Subjects will undergo spirometry according to ATS criteria.

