Initiation visit period 1 (visit 2; Day 1): Subjects meeting entry criteria will be evaluated in the outpatient research unit. CFR-Q will be administered. A limited physical exam will be performed to include vital signs and NER. A urine pregnancy test will be done for females of child-bearing potential. eNO and spirometry will be performed. Spontaneously expectorated sputum will be collected. Safety labs and a sildenafil trough level will be drawn. Each subject will undergo pilocarpine iontophoresis with sweat collection, nasal potential difference testing, and lung clearance index testing. Patient will then receive study medication (placebo or sildenafil.) Subsequent to medication dosing, vital signs will be assessed at 1 hour and 2 hours post-dose. A drop in systolic blood pressure of  $\geq 20$ mmHg will be considered intolerance, and the subject will be discontinued from the study.

Subjects tolerating the medication will be discharged with a 7-day supply of placebo or sildenafil 20 mg p.o. t.i.d. Subjects will be instructed to call the study staff (during business hours) or the pulmonary attending on call (after business hours) for any significant adverse events that occur (e.g. severe headache, dizziness, or persistent visual changes.)

Study visit (visit 3; Day 8 $\pm$ 3): After 7 days of therapy, the subject will return to the study site. Vitals signs and adverse events will be assessed. Safety labs and a sildenafil trough level will be drawn. Each subject will undergo pilocarpine iontophoresis with sweat collection, nasal potential difference testing, and lung clearance index testing. Medication bottles will be collected. Subject will then receive study medication (placebo or sildenafil 40 mg). Subsequent to medication dosing, vital signs will be assessed 1 hour and 2 hours post-dose. A drop in systolic blood pressure of  $\geq 20$ mmHg will be considered intolerance. Subjects with intolerance of dose escalation will be discontinued from the study. Subjects tolerating medication will be given 21 days of placebo or sildenafil 40 mg p.o. t.i.d.

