### Data Analysis

Primary outcome, baseline change in maximal basal PD measurement (mean of 2 nostrils), will be assessed as well as change with amiloride and total change in PD. Secondary outcomes include the mean basal PD, end Ringer's perfusion PD, change with amiloride, change with low chloride, change with isoproterenol, change with low chloride plus isoproterenol, and total change in NPD (delta NPD). Analysis of NPD results will be performed at the Center for CFTR Detection at UAB. All NPD tracings will be interpreted by an independent, blinded investigator, and no scoring will be conducted by the site investigator to prevent biased estimates. All tracings will be scored with electronic assisted data analysis (developed by the UAB Center for CFTR detection). Data for both the primary and the secondary endpoints (other Na and Cl conductance measures by NPD and the concentration of Na and Cl in sweat) will be analyzed separately as a 2X2 crossover design using a repeated measures analysis.

If emerging data from ongoing CFTR modulator trials and NPD measurements obtained using the latest NPD methodology suggests alternative analytic methods (including log transformation) should be used, statistical analysis methods will be updated prior to data base lock and analysis initiation. If these analysis suggests non-normality, rank based analyses (e.g. Mann-Whitney-Wilcoxon rank-sum test or other appropriate test) will be used. Any change in the statistical analysis plan will be finalized before database lock, and reported to the DSMB and CF-TDN PRC. Data will be also be presented using descriptive analyses including individual patient line plots of outcome over time. All patients will be plotted across part one and part two to discern carryover effects.

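### The primary change in maximal basal PD is tied to no visit, although NPD is measured at Day 8 and Day 29, and the only stated model is a crossover analysis that this parallel trial cannot use

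*Combined protocol and SAP*

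**What the plan says.** The Primary Endpoints list gives sodium conductance by NPD, described as "within subject change in maximum basal PD". The Data Analysis section repeats it with one added detail, the averaging of nostrils: "Primary outcome, baseline change in maximal basal PD measurement (mean of 2 nostrils), will be assessed as well as change with amiloride and total change". Neither place gives a day or a visit. (The further measures attached to that sentence are a separate matter; this point concerns visits only.)

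The visit descriptions and the Study Flowchart place NPD at Visit 2 (Day 1), Visit 3 (Day 8) and Visit 4 (Day 29). For Visit 3 the text says "After 7 days of therapy, the subject will return to the study site", and then "Each subject will undergo pilocarpine iontophoresis with sweat collection, nasal potential difference testing, and lung clearance index testing". Those tests are listed before the first 40 mg dose is given. The Dosing section sets the schedule as "20 mg orally t.i.d for the first week, 40 mg orally t.i.d. for the second through fourth weeks". The two post-baseline NPDs therefore follow different doses and different lengths of treatment.

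On the test, the Data Analysis section says that primary and secondary data "will be analyzed separately as a 2X2 crossover design using a repeated measures analysis". On the design, the Randomization section says "Subjects will be randomized in a 2:1 fashion to sildenafil or placebo". There is no second treatment period.

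**The concern.** Each subject has two candidate values for the primary change, and the plan has no rule for choosing between them or combining them. It names no visit contrast, no treatment-by-visit term and no multiplicity rule. The one model it does name has treatment period as its repeated factor. This trial has no such factor, so the stated model cannot settle the question.

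Two things are at stake. If the sponsor could claim success at either visit, the 5% error rate would not hold. If the visits were pooled, the test would keep its size, but the estimate would describe neither the Day 8 nor the Day 29 effect.

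**Working it through.** **Inputs from the Sample size section:** 12 sildenafil and 6 placebo subjects, SD of the change 2.59 mV, planned effect 10.4 mV, 5% level. Sidedness is not stated; two-sided is assumed.

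**Assumptions (not in the documents):** correlation r between the Day 8 and Day 29 changes of 0.3 to 0.9, the same SD at both visits, and the pattern of effect over visits.

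**1. The plan's own figures.** Two-sample t-test on one change per subject, 16 df, critical value 2.120. The standard error is SD × √(1/12 + 1/6) = SD × 0.5.
- Maximal basal PD: noncentrality 10.4 / (2.59 × 0.5) = 8.03. Power is above 99.99%, which matches the stated 100%.
- Sweat chloride: 5 / (2.6 × 0.5) = 3.85. Power is 95.0%, which matches the stated 95%. One-sided and normal-approximation versions give 97.0% to 98.6% and do not match.

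The power statements therefore fit one two-sided comparison of one change score.

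**2. Either visit may count.** Each visit is tested at two-sided 5% with no true effect. With independent tests the error would be 1 − 0.95² = 9.75%. Simulation with correlated changes (12 versus 6) gives:

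| r | Type I error |
|---|---|
| 0.3 | 9.5% |
| 0.5 | 9.2% |
| 0.7 | 8.5% |
| 0.9 | about 7.2% |

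**3. Visits pooled.** The type I error stays at 5%. The pooled effect is (Day 8 effect + Day 29 effect) / 2, and the SD of the mean change is 2.59 × √((1 + r)/2). Take 10.4 mV at Day 29 and zero at Day 8. The target becomes (0 + 10.4)/2 = 5.2 mV, half the Day 29 effect.

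| r | SD of mean (mV) | Noncentrality | Power |
|---|---|---|---|
| 0.3 | 2.09 | 4.98 | 99.7% |
| 0.5 | 2.24 | 4.64 | 99.1% |
| 0.7 | 2.39 | 4.36 | 98.3% |
| 0.9 | 2.52 | 4.12 | 97.1% |

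**4. Smaller effects, for illustration only.** A Day 29 test alone has 90% power at about 4.5 mV. With that effect and r = 0.5, pooled power is about 47%, 65% or 80% if the Day 8 effect is 0%, 25% or 50% of the Day 29 effect. It breaks even at roughly 75%, and reaches about 96% if the two effects are equal. The documents give no time course or dose-response for NPD in patients, so none of these patterns can be preferred.

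**5. One named visit, one contrast.** Type I error is 5%, and power at 10.4 mV is above 99.99%, as in step 1.

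**The case against.** The best case for the plan is that its intent can be inferred. Aim 1 speaks of "conductance by NPD before and after therapy", and the Dosing section describes four weeks of therapy, so the natural reading is Day 1 versus Day 29. The power calculation, built on a single change per subject, points the same way. In addition, NPD tracings are scored blind, and changes to the analysis plan must be final before database lock and reported to the DSMB, which limits opportunistic choice of a visit. All of this stands as evidence of intent. It does not define the test: the Visit 3 text also speaks of therapy completed after 7 days, and nothing says what the model does with the Day 8 value.

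Three stronger readings are tempting, and the documents do not support them:
- **That a repeated-measures analysis must either average over the dose step or give two chances to succeed.** Such a model can equally deliver one Day 29 contrast, or one joint test, at 5%. The plan simply does not say which. Nor is pooling Day 8 with Day 29 its literal text, because the crossover wording refers to treatment periods.
- **That the power calculation contradicts every possible reading.** It fits a test at a single visit.
- **That the trial is underpowered because of this gap.** At the planned effect it is not; the low figures in step 4 need a much smaller effect and an assumed Day 8 shortfall.

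**Conclusion.** The point holds as a gap in the definition of the primary test. Neither the endpoint list nor the analysis section names a visit, two post-baseline NPDs lie on either side of a dose step, and the one stated model does not apply to the design. Correcting the crossover label alone would still leave the visit unnamed.

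Its size is a possible type I error of about 7% to 10% instead of 5% if either visit may count, or an estimate that mixes two doses and durations if the visits are pooled. The error range rests on the assumed correlation of 0.9 to 0.3. It shows what the wording allows; the documents do not show that the sponsor intends to test both visits. It should be settled before database lock.

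**What to change.** In the Primary Endpoints list and the Data Analysis section, replace the crossover model with wording such as:

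*The primary endpoint is the change in maximal basal PD (mean of two nostrils) from Visit 2 (Day 1) to Visit 4 (Day 29). It is tested once, at the two-sided 5% level, as the sildenafil-minus-placebo contrast at Visit 4, from a parallel-group model with treatment, visit, treatment-by-visit and the Day 1 value as covariate. The Visit 3 contrast is secondary.*

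This needs no extra subjects, visits or data, and the Data Analysis section already provides a route for changes before database lock. There is a statistical cost: if the effect is the same at both visits, the Day 29 test has somewhat less power than a pooled test (90% versus about 96% at 4.5 mV and correlation 0.5). If the sponsor wants both visits to count, a split of 2.5% each would hold the overall error at 5% or below and still leave power above 99.99% at 10.4 mV. No view is taken on dose.
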